3. STUDY METHODS AND PROCEDURES

All patients admitted to the TICU will have a documented GCS in the medical chart as a part of clinical care. [name] (LH), the study PI, and the Trauma Intensive Care Unit RN subinvestigators will screen the TICU census daily for new patients to identify those admitted with GCS ≤ 8 that meet study criteria. Eligible patients will be followed by the PI or the TICU RNs until the patient is assessed at GCS of 5 or above.

1. Patients with a GCS of 5 or above will be screened for eligibility. Those eligible will be invited to participate and consent will be obtained by study personnel.
2. Consenting subjects will be randomized to the intervention or control arm of the study

3. For patients randomized to the intervention arm, study personnel (PI or TICU RNs) will request a doctor's referral. A referral will be made to LH who will arrange for the patient to receive the intervention with the dog.
4. The control group will be receiving standard of care bedside interventions. During the control measurement period, the only person present will be the bedside nurse who records the measurements.
5. Study personnel will record the RLAS, GCS, Level of Commands, and Movement of Extremities within 24 hours of obtaining consent and order.

Intervention Group

1. When the patient is randomized to the treatment arm, the PI will refer the case to one of the AAC handler/dog teams approved for work on the study for the intervention. The AAC handler will respond within 3 days and will request data measurements be taken by the bedside RN. These measurements will include (see attachments for data collection sheet):
 - A. RLAS Score
 - B. GCS Score
 - C. Level of Command (LOCmd)-0, 1 or 2 or 3-step
 - D. Movement of Extremities
2. Following the recording of the above measurements, the AAC team will provide AAT to the patient.
3. Immediately following the intervention, the same scores will be measured by the same licensed healthcare professional.

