4. AAT and measurements of the same data will continue up to three times weekly after the initial measurements and will be listed on data collection sheets. If the patient is unavailable for AAT at the time of the scheduled intervention, the research team will document "unavailable," indicate the reason for unavailability. The patient will remain in the study and data collection will continue until the patient is discharged, reaches RLAS 7, or have been hospitalized ≥ 28 days. If the patient has been discharged from the study but remains in the hospital, he/she may continue to receive AAT.

Control Group

1. When the patient is randomized to the control arm, data measurements will be taken by the bedside RN. Variables to be collected include:
 - A. RLAS Score
 - B. GCS Score
 - C. Level of Command-0, 1 or 2 or 3-step (see same data collection sheet).
 - D. Movement of Extremities
2. The control group will be receiving standard of care bedside interventions. During the control measurement period, the only person present will be the bedside nurse who records the measurements. RLAS, GCS, and Level of Command and movement of extremities will be measured by the same licensed healthcare professional before and after each interaction with the healthcare professional.
3. The PI will be responsible for collecting measurements of the same data up to three times weekly after the initial measurements until they are discharged, reach RLAS 7, or have been hospitalized ≥ 28 days.

When the subject is moved to a different unit, study personnel will continue to be responsible for ensuring the study measurements, as measured by the bedside nurse, are recorded on the data collection form.

Methods for Tracking Recruitment and Retention. Study personnel will:

- Screen the trauma services database to determine the number of patients appropriate for the study.
- Keep detailed notes regarding the number of patients identified as potential participants by the study personnel to determine the percentage of eligible patients approached for inclusion into the study to determine the efficacy of our program to treat this population

- Keep detailed logs reflecting the number of patients approached to participate and the reasons for declining participation and for loss to follow up to determine the willingness of participants to consent to participate and remain in the study.

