6. SUBJECT COMPENSATION

6.1. Cost: There are no costs to participants.

6.2. Payment: Participants will not be paid for their participation.

7. ADVERSE EVENT REPORTING: Adverse events will be documented according to IFMC IRB protocol. All adverse events will be reported to the appropriate personnel within the allowed time limit.

8. FUNDING: This is an unfunded, investigator-initiated study.

9. CONFLICTS OF INTEREST: The Animal Assisted Care Coordinator is contracted by Inova Fairfax Hospital Administration to oversee AAI services. The Inova Health Systems Compliance Officer has reviewed the contract and has found no conflicts of interest in the AAC Coordinator being the primary investigator of this study.

10. FACILITIES AND EQUIPMENT: The study setting will be Inova Fairfax Hospital.

11. OUTSIDE CONSULTANTS/COLLABORATORS: There are no outside consultants/collaborators

12. CONTRACTURAL AGREEMENTS: Not applicable.

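### The protocol does not define which control-arm nurse interactions yield the primary ΔRLAS, and does not match their timing to AAT sessions; the choice is left to unblinded staff

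*Protocol*

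**What the plan says.** **AAT arm (Section 3, Intervention Group).** The measured occasion is an identifiable event. "The AAC handler will respond within 3 days and will request data measurements be taken by the bedside RN". The team then gives the session, and the same professional rescores straight afterwards. Sessions and scoring continue up to three times a week. If the patient cannot take part at the scheduled time, this is recorded with the reason. No clock time is given.

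**Control arm (Section 3, Control Group).** Item 1: "When the patient is randomized to the control arm, data measurements will be taken by the bedside RN". Item 2: "During the control measurement period, the only person present will be the bedside nurse who records the measurements", and scores are taken "before and after each interaction with the healthcare professional". Item 3: "The PI will be responsible for collecting measurements of the same data up to three times weekly after the initial measurements". No record of missed control occasions is required.

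**Analysis (Section 4.2).** ΔRLAS is the score during AAT or sham minus the score before it, averaged within each of weeks 1 to 4 and compared by Wilcoxon rank sum test. The word sham appears only in the analysis section. The ΔGCS comparison also uses it, taking chart values from the hour before and the hour after.

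**Who knows the allocation.** "When the patient is randomized to the treatment arm, the PI will refer the case to one of the AAC handler/dog teams", so the PI knows the arm, and no blinding is described. Section 9 identifies the PI as the programme's coordinator and reports that the compliance officer "has found no conflicts of interest in the AAC Coordinator being the primary investigator of this study".

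**The concern.** ΔRLAS measures how much a patient changes over one short encounter. It depends on when that encounter takes place: a patient who is rousable and being stimulated has more room to change than one who is resting. The AAT arm has a recognisable event that starts the measurement. The control arm has only routine nursing contact, with two inconsistent statements of how much of it is scored and none of when.

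If control occasions fall at systematically different times from AAT sessions, or are chosen in a way related to how the patient is doing, the two weekly means differ even when AAT does nothing. The Wilcoxon test would read that difference as a treatment effect. It could favour either arm. No later analysis can recover it, because the occasions that were not scored leave no ΔRLAS.

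**Working it through.** The protocol gives no figure on this point, so there is none to reproduce. The check has three steps.

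**1. Do control items 2 and 3 agree?**

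- If item 2 means every nurse interaction, nothing is selected, but the weekly cap in item 3 is broken.
- If item 3 governs, at most three interactions a week are scored, and the text does not say which.
- If an interaction means a study visit, the items agree on frequency, but that visit is then the sham of 4.2, which Section 3 does not describe.

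No reading fixes the day or hour, or links it to AAT sessions.

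**2. How much room for choice is there if item 3 governs?** Share scored = 3 / (7 × interactions per day).

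- 24 per day, from the hourly GCS recording stated in 4.2: 3/168 = 1.8%
- 8 per day (assumed): 3/56 = 5.4%
- 2 per day (assumed): 3/14 = 21%

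**3. Could timing alone matter?** Simulation with no AAT effect. From the protocol: 50 per arm and three pre/post pairs per patient per week, the stated maximum. Assumed: a two-sided 5% test (the protocol states neither level nor sidedness), ΔRLAS of 0 or +1, independent pairs, and all response rates. AAT pairs respond with probability p. A fraction f of control pairs falls at other hours, with probability q. The control rate is then (1 − f)p + fq. The test compares one week's patient means. Each setting was run with 1,500 to 4,000 replicates; ranges show repeated runs.

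| p | q | f | Control rate | One-week false-positive rate |
|---|---|---|---|---|
| 0.20 | any | 0 | 0.20 | about 5% |
| 0.20 | 0.15 | 0.25 | 0.1875 | about 6% |
| 0.20 | 0.15 | 0.50 | 0.175 | about 8% |
| 0.10 | 0.075 | 0.50 | 0.0875 | about 6% |
| 0.10 | 0.03 | 0.25 | 0.0825 | about 8.5% |
| 0.10 | 0.05 | 0.50 | 0.075 | about 11% |
| 0.20 | 0.05 | 0.25 | 0.1625 | 13–14% |
| 0.10 | 0.03 | 0.50 | 0.065 | 18–19% |
| 0.20 | 0.05 | 0.50 | 0.125 | 40–42% |

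If every control pair fell at other hours (f = 1, p = 0.20), the rate would be about 21% for q = 0.15 and about 66% for q = 0.10.

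All these settings put the lower rate in controls. With equal arms and a two-sided test, exchanging the arms gives the same rejection rate with the false effect against AAT.

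**Selection instead of timing.** Suppose a quarter of control occasions were the lower of two candidate occasions. The rate would be 9%, 14% and 16% for response rates of 0.1, 0.2 and 0.3. With half so chosen, it would be 29%, 44% and 54%. This is a strong assumption, since it needs the chooser to foresee or know both results.

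**The case against.** **A reader might infer that the PI hand-picks control occasions.** The protocol does not say so. Item 3 makes the PI responsible for collecting the data; the bedside nurse takes and records the scores and is the only person present. The paragraph after the control items, on patients who change unit, describes study personnel as ensuring that the nurse's measurements reach the form. That reads as oversight of completeness. Any discretion may lie with the nurse, the PI or both. The nurse knows the arm too, so the gap remains whoever fills it.

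**A reader might infer that AAT timing is fixed and only control timing is free.** This does not stand either. AAT sessions have no stated clock time, are arranged through the PI, and carry the same ceiling of three a week. The protocol gives no visiting hours for the teams. The defect is that the two arms are not matched and that one of them has no defined occasion.

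**A reader might infer partiality from the PI's role.** Naming "the AAC Coordinator being the primary investigator of this study" without the rest of that sentence would mislead, since the reported finding was that there is no conflict of interest. That review nevertheless supplies no rule for choosing occasions.

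**The size is speculative.** This stands. The largest rates with at most half the control pairs unmatched rest on three- to fourfold differences in response between hours, and milder differences give results close to nominal. The simulation shows that the gap can matter, not that bias occurs.

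**The analysis plan could settle it.** It could not. Which occasion is scored is a bedside procedure, and Section 3 already addresses it, inconsistently.

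**Conclusion.** The point holds in this form: Control Group items 2 and 3 are not reconciled, the sham visit behind the primary ΔRLAS is undefined, and nothing matches control occasions to AAT sessions in time. Staff who follow the text as written could produce a discretionary, time-unmatched control sample on the primary endpoint. The ΔGCS comparison inherits the same undefined anchor.

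The direction of any bias is unknown, and the documents do not allow its size to be known. With a quarter to a half of control pairs at unmatched hours, the assumed response rates give a one-week false-positive rate from about 6–8% to about 40%. More extreme assumptions give more. With the same response rate in both arms and no selection, it stays near 5%. The change should be made: it goes to the validity of the primary comparison and is cheap, but nothing in the protocol shows that bias is present.

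**What to change.** In Section 3, replace Control Group items 2 and 3 with one definition of the control (sham) occasion, and use the same term in 4.2:

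- At randomisation, each control patient is given up to three day-and-time slots per week, drawn from the same days and hours in which AAT sessions are scheduled.
- The first routine nurse interaction after a slot opens is scored before and after. No one may move or add an occasion at discretion.
- A missed slot is logged with its reason in both arms, as is already required for AAT.
- In 4.2, AAT sessions that had to be rescheduled stay in ΔRLAS and are flagged. An analysis restricted to on-slot pairs is a sensitivity analysis only, so that sessions moved because a patient was unavailable are not lost from the primary result.

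Cost: a wording change, a slot line on the data collection sheet, some scheduling effort and slightly less flexibility for bedside nurses. No extra staff or measurements are needed. The change removes the timing and selection gap; it does not blind the nurse who scores.

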3.4. Endpoints/Outcome Measures

Patients enrolled in the study will participate until any of the following occurs:

1. choose to no longer participate
2. develop animal allergies
3. reach a RLAS of 7 or above
4. are discharged
5. are hospitalized for greater than or equal to 28 days.

3.5. Consent/Assent: Informed consent will be obtained by the PI or TICU RNs who are sub-investigators on the study. Patients or legally authorized representative of potential subjects will give consent. Patients who do not speak English or Spanish will not be consented.

3.6. Monitoring Subjects and Criteria for Withdrawal of Subjects from the Study.

Criteria for withdrawing subjects from the study are at patient and/or patient LAR request.

4. STATISTICAL CONSIDERATIONS/DATA ANALYSIS

4.1. Sample Size: We estimate that approximately 85% of the patients with TBI will consent for this study. In consideration of the study's endpoints, it is expected that approximately 50 patients will be in each of the two study groups.

4.2. Method of Data Analysis

Aim 1: To determine if the use of animal assisted therapy in the plan of treatment of patients with TBI results in higher scores on the Ranchos Los Amigos, Glasgow Coma Scale, an increased ability to follow commands, and an increased movement of extremities than those who do not receive AAT.

The difference in RLAS scores from pre-intervention to post the intervention will be the primary outcome for the analysis. The outcome, Δ RLAS, will be defined as RLAS during AAT/sham – RLAS pre-AAT/sham. Δ RLAS from each study visit (AAT or sham) will be averaged over each week of the study (weeks 1-4). To address the primary hypothesis, weekly Δ RLAS will be compared between the AAT group and controls using nonparametric Wilcoxon rank sum tests (Mann-Whitney U tests) in order to determine whether the AAT group has significantly higher Δ RLAS. This analysis will be stratified by weeks 1-4 to determine whether the difference in Δ RLAS between AAT and controls changes over time.

The difference in LOCmd scores and movement of extremities will be a secondary outcome of this study. Δ LOCmds and movement of extremities will be defined similarly to Δ RLAS, as the LOCmds and movement of extremities during AAT/sham – LOCmds and movement of extremities pre-AAT/sham, and the mean Δ LOCmds and movement of extremities will be calculated for each week of the intervention (1-4). Weekly

Δ LOCmd scores and movement of extremities will be compared between study groups (AAT vs. controls) using nonparametric Wilcoxon rank sum tests. This analysis will be stratified by weeks 1-4 to determine whether the difference in Δ LOCmd and movement of extremities between AAT and controls changes over time.

GCS scores are routinely collected every hour by the TICU nursing staff. Medical charts will be reviewed to record the GCS scores during the hour immediately before and immediately after the intervention (or sham) is implemented. Δ GCS will be defined as GCS after AAT/sham – GCS pre-AAT/sham. Weekly Δ GCS scores will be compared between study groups (AAT vs. controls) using nonparametric Wilcoxon rank sum tests. This analysis will be stratified by weeks 1-4 to determine whether the difference in Δ GCS between AAT and controls changes over time.

Aim 2: To determine if the use of animal assisted therapy in the plan of treatment of patients with TBI are discharged with a higher degree of cognitive function than those who did not receive AAT.

To address the primary hypothesis, weekly Δ RLAS will be compared between the AAT group and controls using nonparametric Wilcoxon rank sum tests (Mann-Whitney U tests) in order to determine whether the AAT group has significantly higher Δ RLAS. This analysis will be stratified by weeks 1-4 to determine whether the difference in Δ RLAS between AAT and controls changes over time.

The difference in LOCmd scores will be a secondary outcome of this study. Δ LOCmd and movement in extremities will be defined similarly to Δ RLAS, as the LOCmds and movement of extremities during AAT/sham – LOCmds and movement of extremities pre-AAT/sham, and the mean Δ LOCmds and movement of extremities will be calculated for each week of the intervention (1-4). Weekly Δ LOCmd scores and movement of extremities will be compared between study groups (AAT vs. controls) using nonparametric Wilcoxon rank sum tests. This analysis will be stratified by weeks 1-4 to determine whether the difference in Δ LOCmds and movement of extremities between AAT and controls changes over time.

4.3. Data Storage: The data will be stored on a password protected computer in the AAC office for three years in a Microsoft Excel 2010 database and then destroyed. Only study personnel will have access to these data.

4.3.1. Data Management: Information about study subjects will be kept confidential and managed according to the requirements of the Health Insurance Portability and Accountability Act of 1996 (HIPAA). Privacy and confidentiality of all enrolled patients will be maintained. All data collection tools will be taken to the AAC Office and will be entered by LH into the secure study data base. Consent documents and the regulatory binder will be kept in the Trauma Research Manager's office. The Trauma Department suite is locked, and the Trauma Research Manager's office is locked.

4.3.2. Records Retention: The data will be stored for three years in a Microsoft Excel 2010 database and then destroyed.

5. HUMAN SUBJECTS PROTECTION (RISKS, BENEFITS, and ALTERNATIVES)

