1. INTRODUCTION

1.1 .Specific Aims

Aim 1: To determine if the use of animal assisted therapy in the plan of treatment of patients with TBI results in differences in scores on the Ranchos Los Amigos Scale, Glasgow Coma Scale, and in an increased ability to follow commands from those who do not receive AAT.

Aim 2: To determine if the use of animal assisted therapy in the plan of treatment of patients with TBI are discharged with a different degree of cognitive function than those who did not receive AAT.

1.2 .Hypothesis

Hypothesis 1 Patients sustaining TBI who participate in AAT will experience a faster and higher elevation in RLAS, GCS scales and the ability to follow commands than those TBI patients who do not receive AAT.

Hypothesis 2 Patients sustaining TBI who participate in AAT will experience a faster and higher elevation in cognitive function (as evidenced by the ability to follow multiple commands) than those TBI patients who do not receive AAT.

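### ΔRLAS restarts from each session's own pre-score, so it measures acute response; as the only RLAS analysis it does not test faster or higher recovery (Hypothesis 1) or function at discharge (Aim 2)

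*Protocol*

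**What the plan says.** Hypothesis 1 (Protocol 1.2) is about recovery over the stay: "Patients sustaining TBI who participate in AAT will experience a faster and higher elevation in RLAS, GCS scales and the ability to follow commands", compared with patients without AAT. Aim 2 concerns cognitive function at discharge.

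The primary outcome is fixed in 4.2: "The outcome, Δ RLAS, will be defined as RLAS during AAT/sham – RLAS pre-AAT/sham". It is then aggregated: "Δ RLAS from each study visit (AAT or sham) will be averaged over each week of the study (weeks 1-4". The test follows: "weekly Δ RLAS will be compared between the AAT group and controls using nonparametric Wilcoxon rank sum tests (Mann-Whitney U tests". The text under Aim 2 repeats this test and adds the same construction for the secondary scores: "the mean Δ LOCmds and movement of extremities will be calculated for each week of the intervention (1-4". ΔGCS is likewise the score after a session minus the score before it.

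Section 3 confirms that the pre-score is renewed at every session. In the AAT arm the scores come first: "Following the recording of the above measurements, the AAC team will provide AAT to the patient". They are measured again straight afterwards, and the cycle repeats: "AAT and measurements of the same data will continue up to three times weekly after the initial measurements". In the control arm the scores "will be measured by the same licensed healthcare professional before and after each interaction with the healthcare professional".

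An enrolment RLAS, GCS, level of commands and movement score is recorded within 24 hours of consent and order (section 3, step 5). No analysis in 4.2 uses it.

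**The concern.** The hypothesis is about the level a patient reaches and how soon. The statistic is about how far the patient moves within a session. A level gained in one session and kept raises the next pre-score, so it adds nothing to later sessions. A level gained and lost is counted again each time. A level gained between sessions is never counted.

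Two wrong conclusions are then possible. A significant ΔRLAS could be reported as faster recovery when resting RLAS is the same in both arms. A null ΔRLAS could be reported as no effect when AAT patients recover faster between sessions. In addition, 4.2 reads week-to-week differences in the contrast as the effect changing over time, yet a falling weekly Δ can simply mean that earlier gains were kept.

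**Working it through.** The protocol gives about 50 patients per arm and no numerical assumption for ΔRLAS, so there is no figure of the plan to reproduce. The check applies the definition in 4.2 to constructed records and then to simulated trials.

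**Inputs from the protocol.** Up to 3 sessions a week for 4 weeks, so at most 3 × 4 = 12 sessions; exit at RLAS 7; about 50 per arm; Wilcoxon rank sum test by week. **Assumed:** start at RLAS 3, the gain rates below, two-sided 5%.

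**Identity.** Over a patient's sessions, ΣΔ = (last in-session score − first pre-score) − Σ(next pre-score − previous in-session score). The last term is all between-session change, and it is subtracted out.

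**Constructed records.**

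| Patient (start RLAS 3) | Weekly ΔRLAS, weeks 1-4 | Overall mean | Resting level reached |
|---|---|---|---|
| Rises to 4 in every session, falls back each time | 1, 1, 1, 1 | 1.00 | 3 |
| Rises to 4 in session 1 and stays there | 0.33, 0, 0, 0 | 1/12 = 0.08 | 4 |
| Gains and keeps a level in sessions 1, 5 and 9 | 0.33, 0.33, 0.33, 0 | 3/12 = 0.25 | 6 |
| Climbs from 3 to 6 between sessions only | 0, 0, 0, 0 | 0 | 6 |
| Gains and keeps a level in each of 4 sessions, exits at 7 | 1 while in study | 4/4 = 1.00 | 7 |

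The first patient has no lasting recovery and is ranked at or above all the others. The last row is the limiting case: keeping a level at every session ties.

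**Ceiling for kept gains over all 12 sessions.** Ending at RLAS 6 gives (6 − 3)/12 = 0.25. Reaching 7 in session 12 itself gives (7 − 3)/12 = 0.33. The vanishing-gain patient has 1.00.

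**Simulated trials.** 50 per arm, up to 12 sessions, exit only at RLAS 7. Scenarios 1 and 2 used 1,000 trials each, scenario 3 used 300.

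| Scenario (assumed rates, AAT vs control) | Resting rise by week 4 | ΔRLAS test significant, weeks 1-4 | Change from enrolment significant, weeks 1-4 |
|---|---|---|---|
| 1. Transient in-session gain 30% vs 10%; equal recovery | 1.1 vs 1.1 | 99% each week | 4% each week |
| 2. Equal in-session gain; between-session recovery 20% vs 10% per interval | 2.1 vs 1.1 | 4-5% each week | 49%, 85%, 96%, 100% |
| 3. In-session gain 20% vs 10%, all kept; no between-session recovery | about 2.0 vs 1.1 | 64%, 69%, 67%, 69% | 50%, 85%, 96%, 99% |

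Repeat runs gave 98-100% for ΔRLAS in scenario 1, 2-7% in scenario 2 and 62-69% in scenario 3. With kept in-session gains at 30% vs 10%, ΔRLAS is significant in about 99% of trials each week.

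**The case against.** Within-session change is a deliberate and legitimate endpoint. Section 3 is built on scoring just before and just after each session by the same professional, and both the abstract and 4.2 name the pre-to-post difference as primary. It removes differences in level between patients and most spontaneous recovery. Scenario 3 shows that it responds to benefit that lasts, provided the gain arises in a session; in week 1 it does better than change from enrolment (64% vs 50%). All of this stands.

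Three stronger readings are tempting and are not supported:

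- A reader might infer that a patient who stays improved always scores lower. The four-session patient who exits at RLAS 7 ties. The ceilings of 0.25 and 0.33 need all 12 sessions, whereas sessions are only up to three a week and fast recoverers leave early.
- A reader might infer that ΔRLAS is blind to any doubling of recovery. That holds in scenario 2, where AAT acts only between sessions, and fails in scenario 3.
- A reader might infer that the primary outcome must be replaced. That is a design preference. Limiting its conclusion and adding a comparison is enough.

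Change from enrolment has weaknesses too. The enrolment score is timed from consent and order, but section 3, step 3 requests a referral only in the AAT arm, so its timing may differ by arm. Patients leave at discharge, and section 3 anticipates mortality, so a late-week comparison among those remaining is selected.

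One defence fails. The pre-score cannot be read as a single enrolment baseline, because 4.2 takes the difference from each study visit and section 3 has scores taken before each one.

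**Conclusion.** The point holds in this form: the planned statistic measures acute response, and nothing else in 4.2 tests recovery over the stay or function at discharge. A kept gain counts once, between-session recovery counts never, and with one-level gains a patient who stays improved can score below, and at best level with, one whose gain vanishes each time. The same applies to level of commands, movement of extremities and GCS.

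The record-by-record result follows from the definition and needs only the illustrative RLAS values. The percentages rest on assumed gain rates and a common start at RLAS 3. Scenarios 1 and 2 are selected extremes, and no scenario has exits for discharge or death, so the late-week figures for change from enrolment are optimistic. They show that the planned test can go wrong in either direction, not how likely that is in this trial.

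The change should be made because it affects what the trial can conclude. The protocol itself fixes the formula, reference point, averaging and test, so this is not a detail left to a later analysis plan.

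**What to change.** In section 4.2:

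- Keep the within-session Δ, label it acute response during a session, and limit its conclusion to that.
- For Hypothesis 1, add a weekly between-arm Wilcoxon comparison of change from enrolment: the week's last available pre-session score minus the enrolment score. Do this for RLAS and likewise for level of commands, movement and GCS.
- For Aim 2, compare the last recorded score minus the enrolment score. This also picks up a gain that first appears in a patient's final session, which the pre-session score would miss.
- Time the enrolment score from the same event in both arms, and before the first session.
- Carry patients who exit at RLAS 7 as 7 in later weeks, and state a rule for those who leave by discharge or death.

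The scores are already collected in both arms, so no new assessments or patients are needed; only the baseline timing has to be aligned. The cost is rewording, four more weekly tests per score plus the Aim 2 comparison, and a sentence on the status of these tests beside the primary one. Change from enrolment also carries spontaneous recovery and is noisier for a purely acute effect, which is a reason to keep the within-session Δ beside it.
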